8.0 AGENT INFORMATION

8.1 Lazanda®

Please refer to Investigator's Brochure for more comprehensive information.

Other names for the drug: Fentanyl Nasal Spray CII

Mechanism of action (or Product description): Fentanyl is a pure opioid agonist whose principal therapeutic action is analgesia. Pharmacological effects of opioid agonists include anxiolysis, euphoria, feelings of relaxation, respiratory depression, constipation, miosis, cough suppression, and analgesia. Its active ingredient, fentanyl citrate, USP is N-(1-phenethyl-4-

piperidyl) propionanilide citrate (1:1). Fentanyl is a highly lipophilic compound (octanol-water partition coefficient at pH 7.4 is 816.1). Fentanyl citrate is sparingly soluble in water (1:40). The molecular weight of the free base and citrate salt are 336.5 and 528.6, respectively. The pKa is 8.4.

Lazanda nasal spray is a liquid formulation of fentanyl citrate intended for intranasal transmucosal administration. The product consists of a practically clear to clear, colorless, aqueous solution of fentanyl citrate in a glass multidose container to which is attached a metered-dose nasal spray pump with a visual and audible spray counter.

Availability: provided by Depomed, free of charge

How supplied: Lazanda is supplied in glass bottles, containing 8 sprays of 100 mcL containing 100 mcg/100 mcL or 400 mcg/100 mcL concentration solution. Each bottle is supplied in a child-resistant container. Bottles in their child-resistant containers are supplied in cartons containing 1 to 4 bottles. Each carton contains one carbon-lined pouch per bottle for disposal of priming sprays.

Lazanda contains fentanyl, an opioid agonist and a Schedule II controlled substance, with an abuse liability similar to other opioid analgesics. Lazanda[®] can be abused in a manner similar to other opioid agonists, legal or illicit. Because of the risk for misuse, abuse, addiction, and overdose, Lazanda[®] is available only through a restricted program required by the Food and Drug Administration, called a Risk Evaluation and Management Strategy (REMS). Under the Transmucosal Immediate Release Fentanyl (TIRF) REMS Access program, outpatients, healthcare professionals who prescribe to outpatients, pharmacies, and distributors must enroll in this program (see www.TIRFREMSaccess.com). [name], [name], and [name], NP, have all completed their TIRF REMS education and the Moores Cancer Center provides REMS medications.

Prior to initial dosing of Lazanda, subjects will be instructed on the proper use of the study drug product, according to the instructions in **Section 4.2**. Study subjects will receive an initial supply of Lazanda, 1 bottle of 100 mcg spray, at the time of radiation therapy simulation for use during initial dose titration. A single bottle of Lazanda with increments of 100 mcg sprays will provide 8 doses. Subjects will receive additional supply of Lazanda bottles, 5 mL bottles of 100 mcg or 400 mcg or combination of both, at the first radiation treatment visit as determined by the investigator based on opioid needs and the dose established during titration procedures. If the response to the titrated Lazanda dose markedly changes, an adjustment of dose may be necessary to ensure that an appropriate dose is maintained, and may require a refill supply during the course of radiation treatment as determined by dose adjustment and in discussion with the Principal Investigator. All doses will be carefully monitored and recorded and participants will not receive surplus bottles.

Storage and stability: Lazanda will be stored at up to 25C in the Moores Cancer Center Investigational Drug Services (IDS). Do not freeze. Bottles for individual patient use will be returned to the child-resistant container and in the carbon-lined pouch in the cardboard carton for secure storage at home after each use. Lazanda must be stored out of reach of children and protected from light.

Preparation: Bottles containing Lazanda will be supplied in ready-to-use form. No further drug preparation (e.g., reconstitution, dilution) is required by IDS prior to labeling and dispensing.

Route of administration for this study: Lazanda will be administered as an intranasal spray. Each actuation on the metered-dose nasal spray counter is designed to deliver a spray of 100 mcL of solution containing 100 mcg or 400 mcg fentanyl base. This enables doses of 100 mcg or 400 mcg to be administered using a single spray into one nostril (100 mcg), a single spray into each nostril (200 mcg), or two sprays into each nostril (400 mcg), based on the effective and tolerable dose determined through titration steps described in **Section 4.2**.

Side effects: The most commonly observed adverse events (frequency $\geq 5\%$) seen with Lazanda are typical of opioid side effects, such as nausea, vomiting, constipation, dizziness, pyrexia, somnolence and headache. Please refer to the Lazanda Package Insert for additional detail on adverse events experienced less commonly (frequency $\geq 1\%$).

8.1.1 Return and Retention of Study Drug

Patients will return remaining study drug supply to a member of the study team who will log the return with IDS. Remaining drug is to be destroyed on-site, according to UCSD Moores Cancer Center IDS drug destruction policy.

8.1.2 Drug Accountability/Subject Compliance

Records of study medications used, dosages administered, and intervals between visits will be kept during the study. Subjects will be asked to fill out a daily study drug diary while taking Lazanda and bring with them, along with any unused study drug, on each visit to clinic for review with a member of the study team.

Final drug accountability will be noted at the completion of the trial. Patients will be asked to return all unused medication at the end of the study.

9.0 STATISTICAL CONSIDERATIONS

9.1 Study Design/Study Endpoints

This is an open label, single center, phase II case study. The primary endpoint is PID₁₅, the difference in pain intensity as measured by the NRS-11 between the time of laying down on the hard surface (0 minutes) and the pain intensity at 15 minutes after laying down on the hard surface. Secondary endpoints include change in bone pain severity scores as measured on the BPI-sf, and the rate of drug-related adverse events experienced assessed according to the NCI's CTCAE v4.03 toxicity criteria. Exploratory endpoints will include total recumbent time at each fractionation visit measured in minutes, as well as baseline pain intensity score and 24-hour opioid use (oral morphine equivalents).

9.2 Sample Size and Accrual

This trial will enroll approximately 6 subjects meeting the eligibility criteria described above. Conservatively assuming a 10% drop out rate, we will accrue **5 patients**. Many of the study variables are observational and descriptive. These are best analyzed as they relate to the individual participant experience.

Sample size was calculated PASS (NCSS, LLC. Kaysville, Utah).

There is limited literature relating to the change in pain intensity-NRS pain scores in cancer patients. Previous literature has reported the interquartile range (IQR) for the change in pain intensity-NRS pain score across various patient categories. These IQRs ranged between 1 and

3, thus we used and an estimated IQR of 2 to get a standard deviation of 1.48 (by assuming a normal distribution for differences in pain scores)².

Accrual Targets

Accrual Targets			
Ethnic Category	Sex/Gender		
	Females	Males	Total
Hispanic or Latino	1	1	2
Not Hispanic or Latino	6	7	13
Ethnic Category: Total of all subjects	7	8	15
Racial Category			
American Indian or Alaskan Native	0	0	0
Asian	1	1	2
Black or African American	1	1	2
Native Hawaiian or other Pacific Islander	0	0	0
White	5	6	11
Racial Category: Total of all subjects	7	8	15

9.3 Data Analyses Plans

All analyses will be conducted using SAS version 9.4 (Cary, NC, USA).

9.3.1 Primary Analysis

Our primary aim of assessing the change in NRS-11 scores of patients before and after receiving Lazanda will be analyzed using a linear mixed-effects model to account for the repeated daily dosing. We will model the difference in PID from baseline to 15 minutes (PID₁₅) at each radiation simulation and fractionation visit; with a fixed intercept term for time and a subject level random intercept to account for within-patient variability. We will provide descriptive statistics overall and for each treatment day (day 1, ..., n). Descriptive statistics will include mean/standard deviation, min, max and IQR.

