
Statistical Methodology
	
Descriptive statistics will be used to characterize overall pain change (base to 15) and pain change (base to 15) per treatment day (1,...,n).
 
To analyze our secondary aim, change in our secondary aim, change in patient reported pain severity; we will use the BPI-sf. The BPI-sf will be used to calculate "worst pain" (calculated as the arithmetic mean of the four severity items measuring pain severity

	
in the BPI-sf). We will assess changes in BPI-sf using the same approach as our primary aim. Namely, change in BPI-sf “worst pain” score will be analyzed using a linear mixed-effects model to account for the repeated daily dosing. Modeling the difference in BPI-sf from baseline and 15 minutes at each fractionation visit; with a fixed effect for time and a subject level random intercept to account for within-patient variability. Descriptive statistics will be provided for overall pain severity change and pain severity change at each treatment day (1,...,n). As part of our secondary aim we will also provide descriptive statistics for adverse effects associated with Lazanda use utilizing the NCI CTCAE version 4.03 stratified as before and after palliative radiation.
 
Our exploratory aim will assess the impact of Lazanda on treatment delivery efficiency. This will be assessed by comparing treatment delivery efficiency in the Lazanda treated patients to the historic average. To assess this we will quantify each subjects average total time on the treatment table (averaged across each subjects fractionation visits, in minutes). This average will be compared to the clinic’s historic average of 6 minutes using a one-sample t-test of the null hypothesis that the average time on the treatment table for Lazanda study patients equals 6 minutes. As a further exploratory aim we will also consider the effects of baseline pain intensity score, 24-hour opioid use (oral morphine equivalents) and total treatment time at each fraction (minutes) on change in pain intensity (PID₁₅) by including each of them as fixed effects in the linear mixed-effects models.
 
This trial will enroll approximately 6 subjects meeting the eligibility criteria described above. Conservatively assuming a 10% drop out rate, this will leave an analytic sample size of 5.

--	---

SCHEDULE OF EVENTS

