2.0 STUDY OBJECTIVES

2.1 Primary Objectives

Our primary objective is to assess the change in patient reported positional pain intensity (PI) as measured by an 11-point numerical rating scale (NRS-11) in cancer patients with bone metastases assessed at each daily palliative radiation fraction. Our primary objective will be measured using the pain intensity difference (PID) of the NRS-11 between 0 minutes and 15 minutes after laying down on the hard surface ($PID_{15} = PI_0 - PI_{15}$).

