4.2.1 Radiation Simulation Visit(s)

To determine an individual patient's effective and tolerable Lazanda dose, each subject will undergo dose titration during the radiation simulation visit. Lazanda dose for all subjects on study, including those switching from another fentanyl product, will be determined according to the following procedures:

- 15 minutes prior (T-15) to beginning the radiation therapy simulation, subjects will receive an initial dose of 100 mcg (1 spray) of Lazanda in one nostril prior to lying on the CT simulation hard surface.
- If adequate analgesia is obtained within 30 minutes of administration of the 100-mcg single spray, subsequent pain episodes will be treated with this dose.
- If the subject does not experience relief after 30 minutes, he or she may take another 100 mcg in the opposite nostril **but must wait at least 2 hours** (i.e., T-15 + 2 hours) from the first spray before administering this second 100 mcg dose. The subject may delay or reschedule the simulation (within a 14 days period) or radiation delivery to achieve the adequate pain control dose.
- If adequate analgesia is still not achieved, the subject will continue to dose escalate in a step-wise manner at a minimum of 2 hours between each subsequent escalation until adequate analgesia with tolerable side effects is achieved. A maximum of 4 doses or 400 mcg allowed per day.
- Dose titration steps are further detailed in **Table 1**.

Table 1: Lazanda Dose Titration Steps

Lazanda Dose	Using
100 mcg	1 x 100 mcg spray
200 mcg	2 x 100 mcg spray (1 in each nostril)
400 mcg	4 x 100 mcg spray (2 in each nostril, alternate nostrils) or 1 x 400 mcg spray

Each bottle contains a total of 8 sprays. Lazanda bottles come in 100 mcg or 400 mcg dose. If using dose of 100 mcg with the 100-mcg spray, the patient would have total of 8 doses in a single bottle. If using dose of 200 mcg with the 100-mcg spray, the patient would have total of 4 doses in a single bottle. If using dose of 400 mcg with the 100-mcg spray, the patient would have total of 2 doses in a single bottle. Alternately, if using a bottle of the 400-mcg spray at a dose of 400 mcg, the patient would have total of 8 doses in a single bottle.

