Lazanda titration should be done with caution in patients with chronic obstructive pulmonary disease or preexisting medical conditions predisposing them to respiratory depression and in patients susceptible to intracranial effects of CO₂ retention. Caution should also be used in patients on central nervous system (CNS) depressants and potent CYP3A4 inhibitors.

The minimal effective intranasal dose from the radiation therapy simulation will be the dose used as pre-medication prior to any further radiation therapy fractions (up to 10 fractions). Lazanda should be administered 15 (T-15) minutes prior to laying on the hard surface for each simulation visit. If the response to the titrated Lazanda dose markedly changes, an adjustment of dose may be necessary to ensure that an appropriate dose is maintained as deemed by the investigator.

Subjects will be instructed on the proper use of Lazanda as follows:

- 1) Prime the device before use by spraying into the pouch (4 sprays in total). If study drug has not been used for 5 days, re-prime by spraying once.
- 2) Insert the nozzle of the Lazanda bottle a short distance (about ½ inch) into the nose and point towards the bridge of the nose, tilting the bottle slightly.
- 3) Press down firmly on the finger grips until hearing a “click” and the number in the counting window advances by one.

Subjects will also be advised that the fine mist spray is not always felt on the nasal mucous membrane and to rely on the audible click and advancement of the dose counter to confirm a spray have been administered.

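### The primary model can mix titration-visit and fraction readings, and does not name which simulation row counts, how time is coded or which coefficient is the mean PID15

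*Combined protocol and SAP*

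**What the plan says.** **Visits.** Section 9.3.1 models PID15 "at each radiation simulation and fractionation visit; with a fixed intercept term for time and a subject level random intercept". Section 2.1 sets the objective "in cancer patients with bone metastases assessed at each daily palliative radiation fraction", and the synopsis objective has the same scope. For PID15 itself the synopsis methodology gives only descriptive statistics. It then says of the secondary outcome "We will assess changes in BPI-sf using the same approach as our primary aim", and describes that model as "Modeling the difference in BPI-sf from baseline and 15 minutes at each fractionation visit", which leaves simulation out. On the other side, 2.4 collects the primary endpoint at simulation and at every fraction, and 4.1 restates the objective to cover both. Section 6.2 takes PID15 at baseline and each later visit, and 4.1 equates baseline with simulation.

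**Titration.** Under 4.2.1 every patient starts simulation at 100 mcg. "If adequate analgesia is still not achieved, the subject will continue to dose escalate in a step-wise manner". Afterwards, "The minimal effective intranasal dose from the radiation therapy simulation will be the dose used as pre-medication". The NRS log (Appendix I) has separate simulation rows for 100, 200 and 400 mcg; higher rows are marked not applicable when not needed.

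**Time.** Sections 9.3.1 and 9.3.3 give time a fixed intercept. The synopsis BPI-sf model is instead written "with a fixed effect for time and a subject level random intercept to account for within-patient variability". No section says whether time is linear or categorical, where its zero lies, or which coefficient is the reported PID15.

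**The concern.** A simulation reading and a fraction reading need not measure the same thing. A patient who escalates leaves one or two simulation rows at doses found inadequate, whereas fractions start from the dose that titration selected. Section 9.3.1 has no rule choosing among simulation rows and no term separating them from fractions. Two analysts could fit different data sets, and different time terms, and both could claim to follow the plan. With about five patients analysed, one or two who escalated could shift the main result, and the reported coefficient might not be the mean effect during radiation that 2.1 asks about.

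**Working it through.** **Plan's own figures.** SD from an IQR of 2: 2 / (0.6745 + 0.6745) = 2 / 1.349 = 1.483, matching the stated 1.48. Enrolment: 6 × 0.90 = 5.4, rounded down to the stated 5. The sample size itself cannot be re-derived, because alpha, power and a target difference are not given.

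**Inputs.** F = number of fractions (up to 10, section 3.1; 1, 5 and 10 used here). k = simulation rows at doses judged inadequate, 0 to 2 (Appendix I). One further simulation row is assumed to be at the dose carried forward.

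**Step 1: share of inadequate-dose rows, k / (F + 1 + k).**

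| Fractions | k = 0 | k = 1 | k = 2 |
|---|---|---|---|
| 10 | 0/11 = 0% | 1/12 = 8% | 2/13 = 15% |
| 5 | 0/6 = 0% | 1/7 = 14% | 2/8 = 25% |
| 1 | 0/2 = 0% | 1/3 = 33% | 2/4 = 50% |

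**Step 2: pooled mean, [(F + 1)E + kD] / (F + 1 + k).** E is PID15 at effective doses and D is PID15 at inadequate doses. Assumed: E = 3.0 and D = 0 to 2. The 3.0 is the Lazanda mean at 15 minutes cited in section 1.2. It comes from breakthrough pain, not from lying on a treatment table, so it shows scale only. Fractions alone give 3.0.

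| Fractions | k = 1 | k = 2 | Fall |
|---|---|---|---|
| 10 | 2.75–2.92 | 2.54–2.85 | 0.08–0.46 |
| 5 | 2.57–2.86 | 2.25–2.75 | 0.14–0.75 |
| 1 | 2.00–2.67 | 1.50–2.50 | 0.33–1.50 |

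With k = 0 the mean stays at 3.0. The figures apply to one patient, or to the model estimate if all patients share the pattern.

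**Step 3: direction.** Dosing is at T-15 (4.2.1). Under the definition in 2.1, 2.4, 4.1, 6.2 and 9.1, PI0 is scored on lying down, so it is already a post-dose score. (The synopsis objective words the interval as after administration.) If an effective dose brings relief before T0, its PID15 may be small. Assume E = 1.0 and D = 1.5 to 2.0. The pooled mean then rises to 1.04–1.15 (10 fractions), 1.07–1.25 (5) or 1.17–1.50 (1).

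**Step 4: time wording.** Take 5 fractions, k = 2, E = 3, D = 1, the same pattern in every patient, and all simulation rows at time 0.
- Intercept only: (6 × 3 + 2 × 1) / 8 = 2.50.
- Linear time: mean time = 15/8 = 1.875; Sxy = 45 − 8 × 1.875 × 2.5 = 7.5; Sxx = 55 − 8 × 1.875² = 26.875; slope = 0.279; intercept = 2.5 − 0.279 × 1.875 = 1.98.
- Fractions only: 3.0.

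Simulated mixed models (5 patients, 150 runs) gave 2.48, 1.97 and 2.97. With 10 fractions they gave 2.65, 2.19 and 2.96.

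**Step 5: precision.** The 95% half-width for a mean with SD 1.48 and n = 5 is 2.776 × 1.48 / √5 = 1.84 points.

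**The case against.** A reader might infer that the headline PID15 is diluted, because failed-dose rows are in the model. The documents do not support that. The three dose rows are on a collection form, and no section says that all of them enter the analysis. Adequacy is judged on analgesia within 30 minutes of dosing, not on PID15, so a dose can fail without PID15 being zero. Step 3 shows that pooling can also raise the mean.

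Other points on that side also stand:
- Including simulation agrees with 2.4, 4.1 and 6.2, so 9.3.1 is not an isolated slip. The defect is a conflict between sections over which visits count.
- Counting every simulation row as a problem would overstate the share, since the last row is at the dose carried forward.
- The second time wording is written for the BPI-sf and reaches PID15 only through the statement that the approach is the same.
- Fraction readings are not all at one fixed dose either, because 4.2.1 and 8.1 allow later adjustment.
- This is a small case series with no primary test or threshold. Section 9.3.1 also plans statistics by treatment day, which would show fraction values separately. The half-width of 1.84 exceeds every shift shown above.

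None of this says which rows, time coding or coefficient define the overall estimate. Wide sampling error does not settle that, and an uncertain direction is itself a reason to keep the two kinds of reading apart.

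**Conclusion.** The concern holds in a conditional form. Read literally, 9.3.1 allows readings at doses judged inadequate to be averaged with readings at the dose carried forward, while other sections disagree on whether simulation belongs at all. The affected share is at most 15%, 25% or 50% of a patient's readings with 10, 5 or 1 fractions, and nil for anyone whose first dose is adequate. The shift depends wholly on assumed PID15 values, and its sign is not established. The time wording adds a separate ambiguity: in the worked case, where every patient has two inadequate-dose rows, it alone moves the headline from 2.50 to 1.98. The estimate should be called undefined and possibly biased, not diluted.

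**What to change.** In 9.3.1, fit the primary model to fraction visits only, with an intercept and a random patient intercept and no time slope, and name that intercept as the mean PID15. A slope in the primary model would make the intercept depend on where time is centred, so any trend over fractions belongs in a separate model. Report simulation PID15 separately by dose step. Add one sensitivity run that includes the final simulation row at the dose carried forward. Use the same visit set and wording in the synopsis, 2.1, 2.4, 4.1, 6.2 and 9.3.3.

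Cost: wording changes and one usable row per patient leaving the primary model. That is 1 of 11 carried-forward-dose rows with 10 fractions, 1 of 6 with 5, and 1 of 2 with 1, so it matters most for patients with very few fractions; the sensitivity run shows how much. No new data are needed.

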9.3.2 Safety Endpoint

Safety endpoints will be evaluated by monitoring AEs from clinical and laboratory reporting. Adverse events will be classified according to the NCI-CTCAE version 4.03. Trends in the distribution and severity of the AEs across the study groups will be assessed by examining the count of total AEs and count of AEs at each severity level over the course of the subject's participation in the study.

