2.4 Endpoints

The primary endpoint on this study is change in positional pain intensity as measured by NRS-11 pain scores (**Appendix C**) (PID₁₅= PI₀- PI₁₅). Change in NRS-11 pain scores will be calculated from the time of laying down on the hard surface (0 minutes) to the 15-minute time point. NRS-11 (at time 0 and time 15) will be collected at the radiation simulation and at each subsequent radiation therapy visit. The rationale for obtaining a PID at 15 minutes, is based on the reported intranasal fentanyl C_{max} of 15-30 min.

Secondary endpoints include pain severity difference as measured by the Brief Pain Inventory Short Form (BPIsf)¹⁸ (**Appendix D**). We will compare the BPIsf pain scores from the time of laying down on the hard surface (0 minutes) to 15 minutes after laying down at each fractionation visit. As a secondary endpoint we will also examine Lazanda safety, defined as the rate of drug-related adverse events experienced assessed according to the NCI's CTCAE v4.03 toxicity criteria.

Exploratory endpoints will include total recumbent time at each fractionation visit, measured in minutes.

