5.1.11.3 Medication Use Diary

Patients will complete a daily medication use diary as a record of all oral and self-administered medications received from baseline through the end of the post-treatment follow-up period (**Appendix E**). This includes any anticancer therapy, vitamins, homeopathic/herbal remedies, nutritional supplements, opioid medication use, over-the-counter analgesic medication use, and all other over-the-counter “as needed” (prn) and oral medications. A copy of the medication use diary will be collected from the patient by a member of the study team during each visit to clinic or the radiation treatment center, and entries will be recorded on the concomitant medications case report form.

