5.1.11.4 Laxation Diary

Patients will complete a daily laxation diary as a record of the number of daily bowel movements from baseline through the end of the post-treatment follow-up period (**Appendix F**). Participants will be asked to complete this diary even on days where no daily bowel movement has occurred. A member of the study team will collect a copy of the diary from the patient during each visit to clinic or the radiation treatment center.

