5.1.11.5 Patient Nausea/Vomiting Diary

Patients will complete a daily nausea/vomiting diary as a record of the number of daily nausea and vomiting episodes from baseline through the end of the post-treatment follow-up period (**Appendix G**). Participants will be asked to complete this diary even on days where no nausea or vomiting has occurred. A copy of the diary will be collected from the patient by a member of the study team during each visit to clinic or the radiation treatment center.

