9.3.4 Exploratory Analyses

Our exploratory aim will assess the impact of Lazanda on treatment delivery efficiency. This will be assessed by comparing treatment delivery efficiency in the Lazanda treated patients to the historic average. To assess this we will quantify each subjects average total time on the treatment table (averaged across each subjects fractionation visits, in minutes). This average will be compared to the clinic's historic average of 6 minutes using a one-sample t-test of the null hypothesis that the average time on the treatment table for Lazanda study patients equals 6 minutes.

We will also consider the effects of baseline pain intensity score, 24-hour opioid use (oral morphine equivalents) and total treatment time at each fraction (minutes) on the change in pain intensity by including each of them as fixed effects in the linear mixed-effects models for PID₁₅. The use of continuous assessment for each individual participant strengthens the validity of the research.²⁰ Our final case series report will assess the overall effect of the study drug on the participant radiotherapy related pain as determined by NRS-11 scores, BPI-sf results, and AEs.

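### Two daily symptom diaries cover named common harms of the drug, but no endpoint or analysis uses their counts and no step checks them against the adverse event record

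*Combined protocol and SAP*

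**What the plan says.** **Known harms.** Section 8.1 lists as most commonly observed "nausea, vomiting, constipation, dizziness, pyrexia, somnolence and headache". Section 1.2 likewise calls drowsiness, nausea, vomiting and constipation common. Two of the four dose-modification tables in section 4.7 work from the CTCAE grade of nausea/vomiting and of constipation.

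**Diaries.** The nausea/vomiting diary is "a record of the number of daily nausea and vomiting episodes from baseline through the end of the post-treatment follow-up period" (5.1.11.5, form in Appendix G). The laxation diary counts bowel movements over the same period, with a zero entered on days without one (5.1.11.4, Appendix F). On handling, 5.1.11.4 says "A member of the study team will collect a copy of the diary from the patient during each visit", and 5.1.11.5 makes the same provision. Section 4.9 lists both counts among the data to be gathered in the two-day follow-up.

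**Safety endpoint and analysis.** Section 2.4 defines safety as a secondary endpoint, "defined as the rate of drug-related adverse events experienced assessed according to the NCI's CTCAE v4.03 toxicity criteria". Section 9.3.2 says "Safety endpoints will be evaluated by monitoring AEs from clinical and laboratory reporting" and describes the summary as "examining the count of total AEs and count of AEs at each severity level over the course of the subject's participation in the study". Neither section mentions a diary.

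**The concern.** The trial asks seriously ill patients to record two symptoms every day and then gives those records no stated use. They are the most detailed data it will hold on nausea, vomiting and bowel function. They run through days when the patient is not seen, and they need no judgement about cause.

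That last property matters here. Every patient must already be taking opioids of at least 60 mg morphine or equivalent (3.1), and there is no control arm. Whether a given episode of nausea or constipation is due to the study drug is therefore a judgement, and the section 2.4 endpoint, a drug-related rate, depends on it. Per-day counts on dosing and non-dosing days would let a reader see the pattern without relying on attribution. In a case series of about six patients, within-patient detail of this kind is most of what can be offered on tolerability.

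**Working it through.** The plan gives no figure on this point to reproduce, so the check is mainly textual: follow the two diaries from collection to reporting.

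1. **Collected?** Yes. Both are rows in the Schedule of Events at simulation, fractions and follow-up, and both appear in 4.1, 4.9, 5.1.11.4, 5.1.11.5, 5.3.1, 5.3.2 and 5.4.
2. **Entered in the database?** They should be. Section 10.4 defines the study data by reference to the Schedule of Events, sends study data to electronic case report forms and makes a coordinator responsible for entering all of it.
3. **Compared with the AE record?** Not stated. Sections 5.1.11.4 and 5.1.11.5 stop at collecting a copy. Sections 4.7 and 7.1 to 7.2 describe AE grading and monitoring without naming the diaries as a source.
4. **An endpoint?** No. Sections 2.4 and 9.1 list NRS-11 change, BPI-sf change, the drug-related AE rate and recumbent time; 9.1 adds baseline pain score and 24-hour opioid use.
5. **Analysed?** No. The synopsis statistics and sections 6.1, 6.2, 9.3.1, 9.3.2, 9.3.3 and 9.3.4 do not use either count.

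**How much data this concerns.** Let f be the number of fractions. Counting one simulation day, f fraction days and two follow-up days, each diary has at least d = 1 + f + 2 = f + 3 days per patient. Eligibility allows any f up to 10, and Appendix I provides for courses without fractions 6 to 10. Section 9.2 gives about 6 enrolled and 5 analysed.

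| Assumed f, same for all patients | d per patient | 5 patients | 6 patients |
|---|---|---|---|
| 1 | 1 + 1 + 2 = 4 | 20 | 24 |
| 5 | 1 + 5 + 2 = 8 | 40 | 48 |
| 10 | 1 + 10 + 2 = 13 | 65 | 78 |

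These are lower bounds for patients who complete the assumed course and the follow-up, because non-visit days come on top. Sections 5.3.1 and 5.3.2 have the diaries kept daily from simulation to the end of radiation. The gap from simulation to the first fraction is usually under a week (1.1.2) and may be about 14 days (5.3.1). A 10-fraction course at five treatments a week also crosses at least one weekend.

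The table shows how much collected information has no planned summary. It does not estimate how many events the AE record would miss.

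**The case against.** The strongest reply is that AE capture in this protocol is already systematic. AEs are documented at simulation and at every fraction (5.3.1, 5.3.2), monitoring runs from consent to 30 days after the last dose (7.1), and every treated patient is assessed by CTCAE (4.7). Staff collect the diaries at those same visits, so the clinical reporting in 9.3.2 could reasonably include what they read there. Section 9.2 also says many variables are descriptive and best considered patient by patient. This stands as far as it goes. It shows that capture is not left to chance, but it does not supply a diary summary or a stated comparison with the AE record.

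Several stronger readings are tempting, and the documents do not support them:

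- *The diaries never reach a case report form.* A reader might infer this because only the medication diary has its route spelled out ("entries will be recorded on the concomitant medications case report form"). Section 10.4 covers the other diaries through the Schedule of Events.
- *Events ascribed to background opioids drop out of the AE counts.* Section 7.0 defines an AE regardless of relationship to treatment, 9.3.2 counts all AEs, and 10.6 sends the monitoring board every AE whatever its attribution. Attribution can affect only the drug-related rate.
- *Section 9.3.4 confines the final report to three inputs.* The phrase "as determined by NRS-11 scores, BPI-sf results, and AEs" describes how the effect on radiotherapy-related pain will be judged. It does not exclude other content.
- *Tolerability will look better than it was, or hold rules will go unapplied.* Either would require under-recording despite AE documentation at each fraction, and nothing in the documents shows that.
- *Diaries would cure the small sample.* With five or six patients a harm may not appear at all, and diaries kept by the same patients do not change that.

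The diaries also cover only some of the common harms. Drowsiness is named among them and has no diary.

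**Conclusion.** The point holds as a gap in the analysis plan. Two daily diaries on named common harms are collected and should be entered, yet none of the endpoint or analysis sections uses them, and no step reconciles them with the AE record. Followed as written, the plan yields AE counts only. Nausea and bowel function on non-visit days would reach the safety results only if they were reported and recorded as AEs, and the drug-related rate would carry an attribution judgement that the diary counts avoid.

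In size, this means at least f + 3 unsummarised days per patient in each diary for a course of f fractions: 8 at f = 5 and 13 at f = 10. That rests on one simulation day, completion of the course and both follow-up days being recorded. The effect on the reported AE rate cannot be derived from the documents. The conclusion also assumes that clinical reporting in 9.3.2 does not already mean diary review; if the sponsor intends that, the text should say so. This is a worthwhile, inexpensive improvement. It does not affect the primary analysis or the sample size.

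**What to change.** **Section 9.3.2.** Name the laxation and nausea/vomiting diaries as a descriptive safety source beside the AE counts. For each patient, report nausea/vomiting episodes per day and days with no bowel movement, separately for dosing days, non-dosing days and the two follow-up days. Show antiemetic and laxative use from the medication diary alongside, since the counts are hard to interpret without it.

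**Sections 5.1.11.4 and 5.1.11.5.** State that the staff member who collects each diary checks it against the AE log and records gradable events as AEs under the existing CTCAE rules.

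**Cost.** A wording change to the protocol and its statistical section, a diary check at visits where the copy is already collected, and one additional per-patient display for about six patients. Reported nausea or constipation may rise because the check finds entries not previously logged. No dose, hold rule, sample size or error rate changes.
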